8.2 Analysis of data

Microsoft Excel-2007 program World Health Organization 2008 will be used for data management and analysis. Data will be double entered, validated and analysed by two methods: the Kaplan-Meier method and per-protocol analysis in accordance with WHO recommendations. In addition to the reasons for withdrawal listed in section 3.8, patients will be considered withdrawn from the analysis if the PCR results are unclassifiable or if the results of PCR indicate that the failure is due to reinfection with *P. falciparum* or *P. vivax*.

The final analysis and report will include:

- a description of all patients screened and the distribution of reasons for non-inclusion in the study;
- a description of all the patients included in the study;
- the proportion of adverse events and serious adverse events in all the patients included in the study;
- the proportion of patients lost to follow-up or withdrawn, with 95% confidence intervals and a list of reasons for withdrawal;
- the cumulative incidence of success and failure rates at day 28, PCR-uncorrected and PCR-corrected; and
- the proportion of early treatment failure, late clinical failure, late parasitological failure and adequate clinical and parasitological response at day 28, with 95% confidence intervals, PCR-uncorrected and PCR-corrected, as well as gametocyte carriage at each sampling occasion.
- polymorphism of genetic markers related to artesunate + amodiaquine tolerance/resistance.

Guidelines on calculating the cumulative success or failure rate, the proportion of adequate clinical and parasitological response and treatment failure are given in Appendix 9.

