Artesunate + amodiaquine as well as artemether-lumefantrine have previously shown to be safe and highly efficacious, with polymerase chain reaction (PCR) corrected cure rates >90% by day 42 in clinical trials conducted 2003/4 ([name] et al 2005) and 2005 (Holmgren et al 2007) for the treatment of children with uncomplicated *P. falciparum* malaria in Zanzibar. Zanzibar has recently, and in line with WHO recommendations for low transmission settings, introduced as policy for uncomplicated malaria a single low dose of primaquine (0.25 mg/kg), a *P. falciparum* gametocytocidal drug, in addition to standard ATC. However, no recent efficacy data of the presently recommended first-line treatment are available.

The aim of this study is therefore to provide policymakers with updated efficacy and safety data of artesunate + amodiaquine in combination with a single low dose of primaquine (0.25 mg/kg) and data on genetic markers of ACT tolerance/resistance, proposed as an early warning system for development and spread of antimalarial drug resistance, in Zanzibar. The study protocol is based on the new WHO guidelines for surveillance of antimalarial drug efficacy (WHO 2014).

OBJECTIVES

The general objective of this study is to assess the therapeutic efficacy and safety of artesunate + amodiaquine combined with a single low dose of primaquine (0.25 mg/kg) for the treatment of uncomplicated *P. falciparum* malaria patients in Zanzibar.

The specific objectives are:

- to determine the clinical and parasitological efficacy of artesunate + amodiaquine and primaquine in the treatment of uncomplicated *Plasmodium falciparum* infection;
- to differentiate recurrent infections during follow-up, i.e. recrudescence from new infections, by PCR analysis;
- to evaluate the incidence of adverse events, particularly with regards to potential

hematological adverse events of primaquine; and

- to determine the polymorphism of molecular markers associated with artesunate + amodiaquine tolerance/resistance.
- to formulate recommendations, which will enable the Zanzibar Ministry of Health to make informed decisions about whether the current national antimalarial treatment guidelines should be updated or not.
- To determine efficacy rate of the first line treatment compared to the first efficacy trial thirteen years ago.

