8. STATISTICAL METHODS

8.1 Sample size

Sample size calculations is based on an assumed PCR corrected treatment failure rate of artesunate and amodiaquine by day 28 of 5%, a confidence level of 95% and a precision of 5%. This corresponds to a sample of 73 + 20% to account for attrition, in total 90 patients.

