Appendix 9. GUIDELINES FOR ANALYSIS OF RESULTS

	PCR-uncorrected results		
End-point for day X (X = 28 or 42)	Cumulative success or failure rate (Kaplan-Meier analysis)	Proportion (per-protocol analysis)	
Adequate clinical and parasitological response on day X	Success	Success	
Early treatment failure	Failure	Failure	
Late clinical failure before day 7	Failure	Failure	
Late clinical failure or late parasitological failure on or after day 7	Failure	Failure	
Other species infection	Censored day of infection	Excluded from analysis	
Lost to follow-up	Censored last day of follow-up according to timetable	Excluded from analysis	
Withdrawal and protocol violation	Censored last day of follow-up according to timetable before withdrawal or protocol violation	Excluded from analysis	

End-point for day X	PCR-corrected results		
(X = 28 or 42)	Cumulative success or failure rate (Kaplan-Meier analysis)	Proportion (per-protocol analysis)	
Adequate clinical and parasitological response at day X	Success	Success	
Early treatment failure	Failure	Failure	
Late clinical failure before day 7	Failure	Failure	
Late clinical failure or late parasitological failure on or after day 7			
falciparum recrudescence*	Failure	Failure	
falciparum reinfection*	Censored day of reinfection	Excluded from analysis	
other species mixed with falciparum recrudescence	Failure	Failure	
other species mixed with falciparum reinfection	Censored day of reinfection	Excluded from analysis	
other species infection	Censored day of infection	Excluded from analysis	
 undetermined or missing PCR 	Excluded from analysis	Excluded from analysis	
Lost to follow-up	Censored last day of follow-up according to timetable	Excluded from analysis	
Withdrawal and protocol violation	Censored last day of follow-up according to timetable before protocol violation or withdrawal	Excluded from analysis	

^{*} WHO. Methods and techniques for clinical trials on antimalarial drug efficacy: genotyping to identify parasite populations. Geneva, World Health Organization, 2008 (http://www.who.int/malaria/resistance).

REFERENCES

- Bhattarai A et al., Impact of artemisinin-based combination therapy and insecticide-treated nets on malaria burden in Zanzibar. PLoS Med, 2007. 4(11): p. e309.
- Dahlström S et al., Diversity of the sarco/endoplasmic reticulum Ca₂+-ATPase orthologue of Plasmodium falciparum (PfATP6). Infect Genet Evol. 2008 May; 8 (3):340-5. Epub 2008 Feb 15

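### Does section 8.2 need to request 95% confidence intervals for the Kaplan-Meier rates and adverse events, and name an interval method?

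*Combined protocol and SAP*

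**What the plan says.** Section 8.2 states that the data will be "analysed by two methods: the Kaplan-Meier method and per-protocol analysis in accordance with WHO recommendations". It then lists what the final report will contain. Two items carry intervals:

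- "the proportion of patients lost to follow-up or withdrawn, with 95% confidence intervals and a list of reasons for withdrawal"
- the early failure, late failure and adequate-response proportions, ending "adequate clinical and parasitological response at day 28, with 95% confidence intervals, PCR-uncorrected and PCR-corrected"

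Two items carry none:

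- "the cumulative incidence of success and failure rates at day 28, PCR-uncorrected and PCR-corrected"
- "the proportion of adverse events and serious adverse events in all the patients included in the study"

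For calculation guidance, section 8.2 refers to Appendix 9. That appendix says which outcomes count as success or failure, which are excluded and which are censored (for loss to follow-up, "Censored last day of follow-up according to timetable"). It gives no variance or interval formula. Section 8.1 sizes the trial on PCR-corrected failure by day 28, assumed to be 5%, with "a confidence level of 95% and a precision of 5%. This corresponds to a sample of 73", raised to 90 for attrition.

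**The concern.** The list looks uneven. Attrition is to be reported with an interval, while one of the two efficacy analyses and all of the safety results may appear as bare percentages. Yet the trial is sized by the width of a 95% interval, and its aim, stated at the end of the Background, is "to provide policymakers with updated efficacy and safety data". Adverse event incidence, with particular attention to haematological effects of primaquine, is a specific objective.

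Two things could be at stake. A policymaker who reads 0% serious adverse events might take it as evidence of no risk, when 90 patients cannot show that. And because no method is named, an analyst could choose one that behaves badly near zero, which is where a failure rate of about 5% sits.

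**Working it through.** **1. The plan's own figure.** Inputs from section 8.1: failure rate p = 0.05, precision d = 0.05, z = 1.96.

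n = z² p(1 − p) / d² = 1.96² × 0.05 × 0.95 / 0.05² = 72.99, so 73.

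For attrition, 73 × 1.2 = 87.6 and 73 / 0.8 = 91.25; the stated 90 lies between them. The missing interval requests do not touch either number.

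**2. Does the sizing quantity get an interval?** In Appendix 9, the PCR-corrected per-protocol analysis counts every patient who is not excluded as a success (adequate response) or a failure. Total failure is therefore 1 minus the adequate-response proportion. Section 8.2 asks for a 95% interval on that proportion, PCR-corrected. Reflecting its limits gives the interval for failure, so the estimate behind section 8.1 is covered.

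**3. What the Kaplan-Meier interval would add.** Assumed for illustration: 90 enrolled, 90 − 73 = 17 censored, 4 failures.

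- Per protocol: 4/73 = 5.5%, Wilson 2.2% to 13.3%.
- Kaplan-Meier, all 17 censored by day 7 and failures later: 73 at risk, 5.5%, the same interval.
- Kaplan-Meier, 2, 5 and 10 censored on days 7, 14 and 21, with failures 1, 2 and 1 on days 14, 21 and 28: 1 − (87/88)(80/82)(69/70) = 4.9%, interval 1.9% to 12.0%.
- Same censoring, all 4 failures on day 14: 4/88 = 4.5%, interval 1.8% to 11.1%.

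The Kaplan-Meier intervals use the Wilson formula with the effective sample size implied by Greenwood's variance. The estimate depends on when failures occur as well as when patients are censored. Over these cases it runs from 4.5% to 5.5%, and its upper limit from 11.1% to 13.3%. The per-protocol interval is a fair and slightly wide stand-in.

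**4. Choice of method.** 95% limits at 4/73:

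| Method | Lower | Upper |
|---|---|---|
| Jeffreys | 1.9% | 12.5% |
| Wilson | 2.2% | 13.3% |
| Clopper-Pearson | 1.5% | 13.4% |
| Log-log Greenwood (Kaplan-Meier, no censoring) | 2.1% | 13.9% |
| Simple normal (Wald) | 0.3% | 10.7% |

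The first four agree within about 1.4 points at the upper limit. Only the simple normal interval stands apart, and at 0/73 it collapses to zero width, where Wilson gives 0% to 5.0%. No section prescribes it for the analysis.

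**5. Safety.** For 0 of 90, the upper 95% limit is 2.7% (Jeffreys), 4.0% (Clopper-Pearson) or 4.1% (Wilson). The chance of seeing no case of an event with a true rate of 2% is 0.98⁹⁰ = 0.162; at 1% it is 0.99⁹⁰ = 0.405. These two chances follow from the number of patients, and printing an interval would not alter them.

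**The case for a change.** The best argument for a change is that it would cost a few words. The authors wrote the interval requirement into two items, so its absence from the other two can be read as intended. The cited WHO program may print intervals, but nothing in the documents shows that it does, or by which formula. The Kaplan-Meier result has a stand-in; safety has none. And since no method is named, the simple normal interval is not ruled out.

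The textual part of this stands, and so does the point that safety has no substitute interval. The consequence is slight. A report list sets a minimum and does not forbid intervals. A count out of a known number of patients lets any reader compute the limit. The safety item is loosely worded, but its denominator is all included patients, so the natural reading is patients with at least one event. Zero events reported as 0% to 0% is an error an analyst would be expected to notice. Prescribing one formula would be a preference, since Wilson, Clopper-Pearson, Jeffreys and log-log Greenwood are all defensible and close to one another here.

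**Conclusion.** The observation is accurate, but it describes unwritten reporting detail and calls for no change to the plan. Following section 8.2 as it stands gives sound point estimates, and the sizing quantity receives its interval through the per-protocol adequate-response proportion. No stated figure or rule is wrong, and 73 and 90 are unaffected. The trial has a single arm, and sections 8.1 and 8.2 set no hypothesis test or decision threshold that a missing interval could tip.

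The sizes are modest: about 1 point between the Kaplan-Meier and per-protocol estimates in the illustration, about 1.4 points in the upper limit among the sensible methods at 4/73, and an upper limit of roughly 3% to 4% behind a report of no serious adverse events in 90 patients. This rests on the assumed 4 failures and 17 censored patients, on adverse events being counted by patient, and on analysts using an ordinary interval for small proportions.

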8.3 Dissemination of results

At the end of the study, the principal investigator will submit a report on the study and its main outcome. This report will be shared with the Zanzibar Malaria Elimination Programme and the Zanzibar Ministry of Health.

The results of the study will be presented during scientific meetings and submitted for publication in scientific journals.

The patient data will be made available to WWARN, a global database on antimalarial drug efficacy/resistance. To ensure patient confidentially no patient names will be used; instead only the patient identification number, country of original (Zanzibar) and age will be used.

All health facilities and their respective health authorities will be informed about the outcome of the study.

8.4 Amendments to the protocol

After the protocol has been accepted, no change may be made without the agreement of the principal investigator, the sponsor(s) and the ethical review boards.

9. ETHICAL CONSIDERATIONS

9.1 Approval by the national ethical committee

Before the study, official ethical approval to conduct the study will be obtained from Zanzibar Medical Research Ethical Committee (ZAMREC).

9.2 Informed consent

Patients will be included in the study only if they, or a parent or guardian of children give informed consent. The consent request, available in English and translated into Swahili, will be read entirely to the patient, parent or guardian. Details about the trial and its benefits and potential risks will be explained. Once any questions have been answered, a signature will be requested on the document (Appendix 10). If the patient is illiterate, a literate witness must sign; if possible, the signatory will be selected by the participant and will have no connection to the research team. The principal investigator must also obtain the assent of children over the age of 12 years, but their assent should be accompanied by the consent of a parent or guardian. Consent statement for the pregnancy test is also required for female participants of child-bearing age who are sexually active, please see above section 5.2.6.

9.3 Confidentiality

All information on patients will remain confidential and be shared only by the study team. Unique identifiers will be used for computer-based data entry and blood samples. In all cases, the principal investigator will ensure that screening forms, the case report form and the completed identification code list are kept in locked files.

9.4 Health-care services

Free health care throughout follow-up for any illness related to malaria will be provided to the study patients regardless of treatment outcome; this includes any expenses related to hospital admission and to adverse medicine reactions, if required.

When prospective or actual participants are found to have diseases unrelated to malaria, the study team should advise them to obtain, or refer them for, medical care.

Any person who decides not to participate or who cannot be enrolled into the study because he/she does not meet the criteria will be referred to the health facility staff. Such people will be treated with the official first-line treatment, i.e. Artesunate Amodiaquine Winthrop®, once daily for 3 days combined with a single low dose of primaquine (0.25 mg/kg) and followed-up according to the standard of care established by the Zanzibar Ministry of Health and Social Welfare.

If a patient is withdrawn from the study before he/she has completed the full course of the treatment, the clinician must make all necessary arrangements to provide the patient with the full dose of the medicine being tested or in case of intolerance to artesunate + amodiaquine with a full treatment course of artemether 20 mg – lumefantrine 120 mg (Alu) according to body weight at 0, 8, 24, 36, 48, and 60 hours as recommended in the national treatment guidelines.

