3.6 Exclusion criteria

- Presence of general danger signs in children aged under 5 years or signs of severe falciparum malaria according to the definitions of WHO (Appendix 1);
- mono-infection with a Plasmodium species other than *P. falciparum* detected by microscopy;
- presence of febrile conditions other than malaria (e.g. measles, acute lower respiratory tract infection, severe diarrhoea with dehydration) or other known underlying chronic or severe diseases (e.g. severe malanutrition, cardiac, renal and hepatic diseases,

HIV/AIDS);

- regular medication, which may interfere with the study drugs;
- history of hypersensitivity reactions or contraindications to any of the study medicines; and
- preganacy

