4.3 Rescue treatment

If a patient vomits a dose of the study medicine twice, he/she will be withdrawn from the study and receive Artesunate IV (preferred route) or IM p according to national treatment guidelines

Women who are found to be pregnant at enrolment will be treated with tablets quinine 10 mg/kg body weight 8 hourly for 7days if she is in the first trimester or AS 4mg/kg +AQ 10 mg/kg body weight once a day for 3 days if she is in the second and third trimester will be used according to national treatment guidelines.

Any patient with signs of severe or complicated malaria will be hospitalized and receive parenteral therapy with Artesunate according to national treatment guidelines. Initially, an intravenous loading dose of 2.4 mg/kg will be given at admission then at 12 hrs and 24 hrs, thereafter once a day. The total duration of treatment with parenteral Artesunate should be a minimum of 24hrs and a maximum of 7 days if the patient is still unable to tolerate oral medication for up to 7 days. Together with relevant supportive treatment, such as administration of glucose to avoid hypoglycaemia, antipyretic and other physical methods to control fever, blood transfusion if indicated and/or broad spectrum antibiotics if meningitis/septicaemia cannot be ruled out. If the patient is re-infected with malaria species, he/she will receive artesunate 4 mg/kg + amodiaquine 10 mg/kg body weight once daily for 3 days according to the national treatment guidelines.

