5.2.6 Pregnancy test

Female patients aged 15-49 years will be asked about their menstrual history according to standard and context specific case management of women of child-bearing age in Zanzibar.

Women who are found to be pregnant at screening, and thus not enrolled, and estimated to be in the first trimester will be treated with oral quinine 10 mg/kg body weight 8 hourly for 7 days, whereas pregnant women in the second and third trimester will receive artesunate 4 mg/kg + amodiaquine 10 mg/kg treatment once daily for 3 days according to national treatment guidelines.

Female study participants of child-bearing age, defined as above (menstruating women above 49 years also will be considered), will be appropriately counselled about the risks of becoming pregnant and exposing the fetus to the study medicines and encouraged to use barrier methods for contraception during the entire study period.

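### Section 9.4 gives artesunate-amodiaquine plus primaquine to everyone who fails the criteria, which contradicts the quinine rule for first-trimester pregnancy in sections 5.2.6 and 4.3

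*Combined protocol and SAP*

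**What the plan says.** Section 9.4 (Health-care services) covers people who decline and people who cannot be enrolled. A person who "does not meet the criteria will be referred to the health facility staff. Such people will be treated with the official first-line treatment". That treatment is then spelled out as a 3-day course of the fixed-dose artesunate-amodiaquine product, one dose a day, "combined with a single low dose of primaquine (0.25 mg/kg) and followed-up according to the standard of care". The sentence contains no exception and no cross-reference. The next paragraph of 9.4 offers an alternative, "or in case of intolerance to artesunate + amodiaquine with a full treatment course of artemether 20 mg" with lumefantrine, but only for patients withdrawn before finishing treatment.

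Other sections give specific rules for some of the same people:

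- **Pregnancy, section 5.2.6.** Women found "pregnant at screening, and thus not enrolled, and estimated to be in the first trimester will be treated with oral quinine"; the course lasts a week. The rule for later pregnancy is that "pregnant women in the second and third trimester will receive artesunate 4 mg/kg + amodiaquine 10 mg/kg treatment once daily for 3 days".
- **Pregnancy, section 4.3.** "Women who are found to be pregnant at enrolment will be treated with tablets quinine 10 mg/kg body weight 8 hourly for 7days". This applies in the first trimester. In the later trimesters artesunate-amodiaquine is given. Primaquine is not listed in either case.
- **Severe malaria, sections 3.6 and 4.3.** Section 3.6 excludes patients for "Presence of general danger signs in children aged under 5 years or signs of severe falciparum malaria". Section 4.3 adds: "Any patient with signs of severe or complicated malaria will be hospitalized and receive parenteral therapy with Artesunate". Appendix 6 calls for referral of severe cases and danger signs at day 0.
- **Hypersensitivity or contraindication, section 3.6.** A history of either, for any study medicine, is an exclusion.

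**The concern.** Section 9.4 is the protocol's general rule for people who are screened but not enrolled. Screening runs through 14 primary care facilities, and ineligible people are handed to facility staff. A member of staff who relied on 9.4 alone would give a first-trimester woman artesunate-amodiaquine and primaquine, where two other sections prescribe quinine. This is more than missing detail: a stated rule, if followed, produces a treatment that the same protocol rules out for that woman. What is at stake is the safety of a small group outside the trial population, not the trial's inference.

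**Working it through.** No arithmetic applies. The check compares the rules that reach the same unenrolled person.

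**1. Who falls under section 9.4.** The trigger is failure to meet the criteria. Pregnancy, severe malaria or danger signs, and hypersensitivity or contraindication are all exclusions in 3.6, so all of these people are within the sentence as worded.

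**2. What each rule gives them.**

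| Person not enrolled | Section 9.4 | Specific text | Result |
|---|---|---|---|
| Pregnant, first trimester | Artesunate-amodiaquine + primaquine | Oral quinine for 7 days (5.2.6, 4.3) | Direct contradiction |
| Pregnant, second or third trimester | Artesunate-amodiaquine + primaquine | Artesunate-amodiaquine, primaquine not listed (5.2.6, 4.3) | Differs on primaquine only; nothing expressly forbids it |
| Severe malaria | Artesunate-amodiaquine + primaquine, both oral | Admission and parenteral artesunate (4.3) | Conflict on a literal reading, softened by the Background |
| Danger signs without severe malaria | Referral to facility staff, then the same drugs | Referral at day 0 (Appendix 6); 4.3 does not mention danger signs | No separate drug rule to conflict with |
| Hypersensitivity or contraindication to artesunate-amodiaquine | The same drugs | Artemether-lumefantrine for known intolerance (Background) | Gap largely filled |
| Hypersensitivity or contraindication to primaquine | Primaquine | Nothing | Gap unaddressed |

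**3. Is the first-trimester overlap real?** Yes. Section 5.2.6 names women who are pregnant at screening and therefore not enrolled, which is the group that 9.4 describes in general terms.

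**4. Does any text set precedence?** No. Section 9.4 does not refer to 4.3 or 5.2.6, and neither of those refers to 9.4.

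**5. Does standard of care supply the exception?** Not clearly. In 9.4 those words follow the verb for follow-up, after the drugs have already been specified. Section 6.2 words the matter more broadly, placing examination, treatment and follow-up all under the standard of care, but it addresses only people who decide not to take part.

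**6. Effect on the trial.** The people concerned are never enrolled and contribute no outcome to the Kaplan-Meier or per-protocol analysis. The planned 90 patients are unaffected.

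**The case against.** The strongest reply is that the specific text already governs. Section 5.2.6 deals with exactly these women, trimester by trimester. Section 4.3 speaks of any patient with severe malaria, and Appendix 6 places referral at the first screening step. Section 9.4 is an access-to-care paragraph in the ethics chapter. It can hardly be an exhaustive prescribing rule: taken literally, failing the criteria would include failing an inclusion criterion, such as having no parasites or being unable to swallow tablets. Section 6.1 also treats patients with another febrile illness for malaria only if they have parasitaemia.

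Much of this stands. A sensible clinician would let the specific rule prevail, so actual harm is unlikely. But the protocol does not state that precedence, and the first-trimester contradiction remains on the page.

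The reply goes further on the other limbs. A reader might infer that the protocol sends severely ill patients home with oral tablets. The documents do not support that: the Background describes artesunate-amodiaquine as first-line for uncomplicated malaria and names injectable artesunate for severe malaria. A reader might also infer that people intolerant of artesunate-amodiaquine are left without an alternative. The Background names artemether-lumefantrine for them and does not confine it to withdrawn patients.

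**Conclusion.** The point holds as a minor patient-safety inconsistency. The firm part is first-trimester pregnancy, where 9.4 prescribes one regimen and 5.2.6 and 4.3 another. In the second and third trimesters the difference is only that primaquine is not listed. It would be tempting to call primaquine prohibited there, but no section says so. The severe-malaria and artesunate-amodiaquine hypersensitivity limbs are literal readings that the Background largely answers. Contraindication to primaquine is the one case that nothing addresses.

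The size cannot be put as a number: screening volumes and the share of pregnant or contraindicated people are not given. There is no effect on the endpoint, sample size or analysis. The conclusion assumes that standard of care in 9.4 governs follow-up rather than choice of drug. If it governed both, the contradiction would soften but not disappear, because the drugs are still named without exception.

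**What to change.** In section 9.4, limit the first-line sentence to people with uncomplicated *P. falciparum* malaria and no contraindication to the medicines. Then add these exceptions:

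- pregnant women: treat per 5.2.6;
- patients with severe malaria: treat per 4.3;
- patients with danger signs: refer per Appendix 6 (not 4.3, which does not mention them);
- people with hypersensitivity or a contraindication to a study medicine, including primaquine: alternative per national guidelines.

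Close with a sentence stating that 4.3 and 5.2.6 prevail over this paragraph. The clinical team should settle the treatment content, including whether primaquine is to be withheld throughout pregnancy, and say so explicitly.

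The cost is a few lines of text in one section, agreed under the amendment procedure in section 8.4. Visits, sample size and analysis do not change.
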